8.5. Safety Review Committee

The SRC is composed of the medical monitor, clinical scientist, biostatistician, pharmacovigilance representative, clinical pharmacologist, and investigator. The membership, schedule of meetings, data required for each safety review, and requirements for documenting meeting discussions and outcome will be outlined in the SRC charter.

In order to perform its primary function of ensuring subject safety, the members of the SRC will have access to all safety and clinical data.

The SRC will review the first 48 hours of post-dose clinical safety data for the 6 subjects randomly assigned into Cohort 1a before enrollment into Cohorts 1b or 2 may begin. This will allow for further assessment of safety and tolerability of the SC formulation before exposing additional subjects to ALXN1210 SC. After the SRC has reviewed the safety and clinical data of the last completed subject in Cohort 1a, subjects will be randomly assigned into Cohort 1b in a blinded fashion, to receive either a single 400-mg dose of ALXN1210 SC or a single dose of placebo. In parallel, subjects will be randomly assigned into Cohort 2 to receive a single 400-mg dose of ALXN1210 IV in an open-label fashion.

The SRC will convene to review safety data if unexpected safety concerns arise. The SRC will conduct a review of the clinical and safety data of individual subjects if prespecified criteria as described in Table 3 are met that warrant suspension of the study.

The SRC may make recommendations regarding safety issues, study conduct, and modifying (ie, exploring the dose cohort further, suspending dose cohort[s]), or stopping the study.

8.6. Criteria for Study Termination

The investigator, competent authority, or sponsor may terminate the study for reasonable cause. Conditions that warrant termination of the study include, but are not limited to, the following:

- Discovery of an unexpected, serious, or unacceptable risk to subjects enrolled in the study
- Decision on the part of the sponsor to suspend or discontinue testing, evaluation, or development of the study drug
- Failure of the investigator to comply with the approved protocol, pertinent guidelines, and/or regulations
- Submission of knowingly false information from the investigator to the sponsor and/or regulatory authorities

The end of the study will be defined as the date of the last subject's last visit.

9. SCHEDULE OF ASSESSMENTS

The timing of study procedures is provided in the Schedule of Assessments (Table 4 and Table 5).

Table 4:Schedule of Assessments: Screening through Visit 1

	Visit 1												
Study Day	Screening	Day -1					Day 1				Day 2	Day 3	Day 5
Assessments ¹	Day -70 to Day -2	Admit Day –1	Pre- dose	0 h (SOI)	EOI ²	15 min post EOI	30 min post EOI	2 h post SOI	4 h post SOI	8 h post SOI	24 h	48 h	96 h
Status (OP or CRU)	OP	Admit	CRU	CRU	CRU	CRU	CRU	CRU	CRU	CRU	CRU	CRU	CRU ³
Informed consent ⁴	Х												
MCV4 immunization (Day -56) ⁵	Х												
Meningococcal serogroup B immunization (Day -56 and Day -28) ⁵	Х												
Serum bactericidal antibody (meningococcal serogroups A, C, W135, and Y)	X												
Medical history & demographics	Х												
Physical examination	Х	Х											Х
Height, weight, and BMI	Х												
QuantiFERON [®] -TB test	Х												
Chemistry	Х	Х									Х		Х
Hematology	Х	Х									Х		Х
Coagulation	Х	Х									Х		Х
Hepatitis B and C screen	Х												
HIV, types I and II screen	Х												
Complement activity ⁶	Х												
CH50 ⁷		Х											
Serum pregnancy test ⁸	Х	Х											
Alcohol breath test	Х	Х											
Urinalysis and urine chemistry	Х	Х									Х		Х
Urine drug screen	X	Х											
Vital sign measurements	Х	Х	X ⁹		Х		X ⁹	X ⁹	X ⁹	X ⁹	Х	Х	Х
ECG	Х		X ¹⁰			Х					Х	Х	Х
Cardiac telemetry ¹¹			Х	Х	(X)	(X)	(X)	(X)					
Randomization				Х									
Study drug administration				Х									
PK samples			Х		Х		Х	Х	Х	Х	Х	Х	Х
PD panel (serum C5, cRBC hemolysis)		Х	Х		Х		Х	Х	Х	Х	Х	Х	Х
Infusion site evaluation ¹²			Х				Х	Х	Х	Х	Х	Х	
Immunogenicity (ADA)			Х										
Review potential safety risks of ALXN1210 ¹³	Х	Х											Х

		Visit 1											
Study Day	Screening	Day -1		Day 1 Day 2 Day 3						Day 3	Day 5		
Assessments ¹	Day -70	Admit	Pre-	0 h	EOI ²	15 min	30 min	2 h	4 h	8 h	24 h	48 h	96 h
	to Day -2	Day –1	dose	(SOI)		post	post	post	post	post			
						EOI	EOI	SOI	SOI	SOI			
Status (OP or CRU)	OP	Admit	CRU	CRU	CRU	CRU	CRU	CRU	CRU	CRU	CRU	CRU	CRU ³
Concomitant medications		$\leftarrow Monitor \ continuously \ (after \ ICF \ is \ signed \ at \ screening) \rightarrow$											
Adverse events ¹⁴		$\leftarrow Monitor \ continuously \ (after \ ICF \ is \ signed \ at \ screening) \rightarrow$											
Antibiotic prophylactic treatment ¹⁵		←Antibiotic prophylaxis→											

¹ Permissible windows for study assessments are described in the study operations manual. ² EOI will be approximately 15 minutes after SOI.

³ Subject will be discharged from CRU after completing all Day 5 assessments. Subjects will be provided a "Study Participant ID card" with information for Healthcare Provider and participant on symptoms of meningitis infection.

⁴ Signed and dated EC-approved ICF must be obtained before any study-specific screening procedures are performed.

⁵ For subjects who do not have adequate documentation of prior MCV4 immunization or serogroup B vaccination, MCV4 immunization will be performed at least 56 days prior to first dose on Day 1, and vaccination for serogroup B meningococcal infections will be administered at least 56 days prior to Day 1 dosing with a booster administered at least 28 days prior to dosing on Day 1.

⁶ Complement activity, confirmed by a suitable assay such as complement alternative pathway (CAP) ELISA/C5 (hemolysis) inhibition, will be performed at screening to confirm subjects do not have a complement deficiency.

⁷ The sample drawn on Day -1 will be stored for future analysis should the post-dose sample indicate that complement has not normalized.

⁸ Serum pregnancy test for all female subjects to confirm a female subject is not pregnant.

⁹ On Dav 1, vital sign measurements will be assessed pre-dose (within 15 minutes prior to SOI) and at EOI, 30 minutes after EOI, 2 hours after SOI, 4 hours after SOI, and 8 hours after SOI.

¹⁰On Day 1, triplicate 12-lead ECGs will be performed pre-dose and approximately 15 minutes post-EOI.

¹¹Continuous cardiac registration predose through duration of IV infusion (Cohort 2) and until 3 hours post SC injection (Cohorts 1a and 1b).

¹²Infusion or injection site evaluations will be done within 15 minutes of the start of infusion/injection and \pm 15 minutes of the other scheduled times on Day 1. Indurations or reactions < 1cm will not be listed as an adverse event unless it persists for more than 24 hr. Pain at site of infusion or injection will be assessed using a Visual Analog Scale (0-10). Pain will not be assessed pre-dose.

¹³The investigator or designee will meet with the subject at each visit to discuss the potential safety risks of ALXN1210, and to address any safety concerns on the part of the subject.

¹⁴Collection of AEs and SAEs will begin at ICF signing.

¹⁵ Subjects will be administered prophylactic antibiotic treatment, oral penicillin V 500 mg twice daily (equivalent to 1×10^6 units), beginning on the evening of Day -1, until complement activity has normalized, as determined by CH50 assay.

Abbreviations: ADA = antidrug antibody; BMI = body mass index; cRBC = chicken red blood cell; CRU = clinical research unit; ECG = electrocardiogram;

EOI = end-of-infusion/injection; HIV = human immunodeficiency virus; ICF = informed consent form; MCV4 = tetravalent meningococcal conjugate vaccine;

OP = outpatient; SOI = start-of-infusion/injection; TB = tuberculosis

	Visit 2	Visit 3	Visit 4	Visit 5	Visit 6	Visit 7	Visit 8	Visit 9	Visit	Visit	Visit 12	Visit 13	Visit 14
Procedures	Day 8	Day 15	Day 22	Day 29	Day 36	Day 43	Day 50	Day 57	Day 71	Day 90	Day 120	Day 150	Day 200
Status (OP or CRU)	OP	OP	OP	OP	OP	OP	OP	OP	OP	OP	OP	OP	OP
Physical Examination		Х				Х				Х	Х	Х	Х
Vital Sign Measurements	Х	Х	Х	Х	Х	Х	Х	Х	Х	Х	Х	Х	Х
ECG												Х	Х
Chemistry	Х	Х		Х		Х		Х		Х	Х	Х	Х
Hematology	Х	Х		Х		Х		Х		Х	Х	Х	Х
Coagulation	Х	Х		Х		Х		Х		Х	Х	Х	X
Urinalysis and Urine Chemistry		Х				Х				Х	Х	Х	X
Serum Pregnancy Test												Х	Х
CH50 Testing						Х		X ¹					
Pharmacokinetic Samples	Х	Х	Х	Х	Х	Х	Х	Х	Х	Х	Х	Х	X
Pharmacodynamics Panel (serum C5, cRBC hemolysis)	Х	Х	Х	Х	Х	Х	Х	Х	Х	Х	Х	Х	Х
Immunogenicity (ADA)		Х		Х				Х		Х	Х	Х	Х
Review Potential Safety Risks of ALXN1210 ²		← Discuss potential safety risks of ALXN1210→											
Concomitant Medications				÷	Monitor	continuou	sly (after I	CF is signe	ed at screer	ning)→			
Adverse Events ³		← Monitor continuously (after ICF is signed at screening)→											
Antibiotic Prophylactic ⁴						← A	ntibiotic pr	ophylaxis-	-→				

Table 5:Schedule of Assessments: Visit 2 through Visit 14

¹ Additional samples may be taken after Day 57 as per Section 5.1.4.1.

² The investigator or designee will meet with the subject at each visit to discuss the potential safety risks of ALXN1210, and to address any safety concerns on the part of the subject.

³ Collection of adverse events will begin at ICF signing.

⁴ Subjects will be administered prophylactic antibiotic treatment, oral penicillin V 500 mg twice daily (equivalent to 1×10^6 units) until complement activity has normalized, as determined by CH50 assay.

Abbreviations: ADA = antidrug antibody; cRBC = chicken red blood cell; CRU = clinical research unit; ECG = electrocardiogram; ICF = informed consent form; OP = outpatient

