5.1.1. Clinical Studies

ALXN1210 has been administered safely to healthy subjects in 200 mg and 400 mg intravenous (IV) doses in a single ascending dose (SAD) study (Study ALXN1210-HV-101, N = 10). Healthy subjects have also been administered multiple 400 mg and 800 mg IV doses on an every 4 week (Q4W) regimen in an ongoing multiple ascending dose (MAD) study (Study ALXN1210-HV-102, N = 12). The starting doses of ALXN1210 IV in these 2 healthy volunteer studies were selected to assess safety in healthy volunteers and to have measurable pharmacologic activity (eg, inhibition of complement activation) based on the therapeutic exposure required with eculizumab. No safety concerns have been identified in either of the Phase 1 studies, both of which were randomized, blinded, and placebo controlled. In the completed Study ALXN1210-HV-101 (SAD), no serious adverse drug reactions, treatment discontinuations, or deaths were reported.

Conclusions from Study ALXN1210-HV-101 are as follows:

- ALXN1210 exhibited prolonged pharmacokinetic (PK) exposure with mean geometric half-life estimates of 32.4 days and 30.8 days following single doses of 200 and 400 mg, respectively.
- The PK parameters (area under the serum concentration versus time curve from time zero to the last quantifiable concentration $[AUC_t]$, area under the curve from time zero to infinity $[AUC_{\infty}]$, and maximum observed serum concentration $[C_{max}]$) increased in a slightly less than dose-proportional manner over the studied range of 200 to 400 mg based on the protocol-specified statistical analysis.

- Following single 200 mg and 400 mg doses of ALXN1210 IV, all 6
 pharmacodynamic (PD) variables (total complement C5 serum concentration, free
 complement C5 serum concentration, chicken red blood cell [cRBC] hemolysis,
 classical complement pathway [CCP] activity, complement alternative pathway
 [CAP] activity, and plasma C5b-9 activity) showed dose-dependent reductions from
 baseline. The effect of ALXN1210 on these PD variables was immediately evident
 after end of infusion (EOI). At the EOI, the mean free C5 serum concentrations and
 cRBC hemolysis activity were inhibited by > 99% and > 97%, respectively.
- The duration of the effect was longer following a 400-mg dose than a 200-mg dose.
- All subjects were negative for antidrug antibody (ADA) through Day 150.

In addition, multiple doses of ALXN1210 IV have been administered to patients with PNH.

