8.3. Dose Rationale

8.3.1. ALXN1210 IV Dose

The geometric mean (coefficient of variation [CV]) ALXN1210 half-life in Study ALXN1210-HV-101 ranged from 30.8 (10.2%) to 32.4 (16.2%) days over the studied doses. Following single 200-mg and 400-mg doses of ALXN1210 IV to healthy volunteers, all studied PD variables showed dose-dependent changes from baseline that recovered back to baseline. The effect of ALXN1210 on these PD variables was immediately evident after EOI. At the EOI, the mean free C5 serum concentrations and cRBC hemolysis activity were inhibited by > 99% and > 97%, respectively. In the ongoing Study ALXN1210-HV-102, 400-mg and 800-mg (Q4W) doses of ALXN1210 IV are being studied to assess safety, tolerability, PK, PD, and immunogenicity in healthy volunteers.

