10. SELECTION AND WITHDRAWAL OF SUBJECTS

10.1. Subject Inclusion Criteria

Subjects must meet all of the following criteria in order to be eligible for the study:

- 1. Healthy subjects, aged 25 through 55 years, inclusive, at the time of dosing.
- 2. Body mass index (BMI) from 18 through 29.9 kg/m², inclusive, and weight between 50 and 100 kg, inclusive.
- 3. QT interval corrected using the Fridericia's formula (QTcF) \leq 450 msec for males and \leq 470 msec for females at screening and prior to dosing on Day 1.
- 4. Willing and able to give written informed consent and comply with the study visit schedule.
- 5. Documented vaccination with MCV4 at least 56 days and not more than 3 years prior to dosing. Documentation must include a positive SBA titer to confirm an immune response before study drug administration.
- 6. Vaccination with serogroup B meningococcal vaccine at least 56 days prior to dosing on Day 1, with a booster administered at least 28 days prior to dosing on Day 1, with at least 28 days between the first and second injections.
- 7. Female subjects of childbearing potential, if heterosexually active, must use highly effective or acceptable contraception as defined below, starting at screening and continuing until at least 6 months after study drug administration. Antibiotic prophylaxis is required during this study, which can compromise the efficacy of hormonal contraception. Therefore, it is recommended that subjects using hormonal contraception also use barrier contraception (eg, condom or diaphragm with spermicide) for the duration of antibiotic prophylaxis.

Highly effective contraceptive methods for females are as follows:

- Combined (estrogen- and progestogen-containing) hormonal contraception associated with inhibition of ovulation as follows:
 - Oral
 - Intravaginal
 - Transdermal
- Progestogen-only hormonal contraception associated with inhibition of ovulation as follows:
 - Oral
 - Injectable
 - Implantable
- Intrauterine device

- Intrauterine hormone-releasing system
- Bilateral tubal occlusion

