- 9. Positive or indeterminate QuantiFERON[®]-TB test indicating possible tuberculosis (TB) infection.
- 10. History of latent or active TB or exposure to endemic areas within 8 weeks prior to the screening visit.
- 11. Female subjects who are breastfeeding or are heterosexually active and unwilling to practice contraception and are not postmenopausal. Postmenopausal is defined as amenorrhea ≥ 12 consecutive months without another cause and a documented serum follicle-stimulating hormone level ≥ 40 mIU/mL and estradiol concentration ≤ 110 pmol/L within the 6 months prior to study drug administration.
- 12. Positive serum pregnancy test at screening or on Day -1.
- 13. Serum creatinine greater than the upper limit of normal (ULN) of the reference range of the testing laboratory at screening or on Day –1.
- 14. Alanine aminotransferase (ALT) or aspartate aminotransferase (AST) > ULN of the reference range of the testing laboratory at screening or > $1.5 \times$ ULN of the reference range of the testing laboratory on Day -1.
- 15. Any of the following hematology results: hemoglobin < 130 g/L for males and < 115 g/L for females, hematocrit < 0.37 L/L for males and < 0.33 L/L for females, white blood cell (WBC) count < $3.0 \times 10^3/\mu$ L, absolute neutrophil count < $2.0 \times 10^3/\mu$ L, and platelet count < 150 or > 400 × 10³/\muL at screening or on Day –1. Complete blood count (CBC) clinical laboratory results that are considered clinically relevant and unacceptable by the investigator at Day –1.
- 16. History of complement deficiency or complement activity below the normal reference range as evaluated by CAP ELISA at screening.
- 17. History of malignancy with the exception of a nonmelanoma skin cancer or carcinoma in situ of the cervix that has been treated with no evidence of recurrence.

- 18. Participation in a clinical study within 30 days before initiation of dosing on Day 1 or use of any experimental small-molecule therapy within 30 days prior to dosing on Day 1.
- 19. Participation in more than one clinical study of an mAb, or participation in a clinical study of an mAb within the 12 months prior to screening, during which the subject was exposed to the active study drug. Subjects who have participated in only one study of a mAb may be considered for enrollment if they completed that study more than 12 months prior to screening.
- 20. Prior exposure to ALXN1210.
- 21. Major surgery or hospitalization within 90 days prior to dosing.

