15.1.6.7. Pregnancy Testing

Pregnancy testing (beta human chorionic gonadotropin) will be performed in all female subjects (Section 16.8). The timing of pregnancy testing is described in Schedule of Assessments (Section 9).

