16.8. Exposure During Pregnancy and Lactation

Pregnancy data will be collected during this study for all subjects.

For all Alexion products, both in development or postapproval, exposure during pregnancy must be recorded and followed. Exposure during pregnancy, also called exposure in utero, can be the result of either maternal exposure or transmission of drug product via semen following paternal exposure.

If a female subject participating in this study or a male subject's female partner becomes or is found to be pregnant while being treated or exposed to study drug, the investigator must submit the "Pregnancy Reporting and Outcome/Breast Feeding Form" to Alexion or designee via the same methods as SAE reporting. Female subjects who become pregnant will be discontinued from dosing, but will continue to be followed for safety where feasible. Male subjects may

continue in the study if an accidental pregnancy of their female partner occurs despite adequate contraception.

The female subject should be followed until the outcome of the pregnancy is known (spontaneous miscarriage, elective termination, normal birth or congenital abnormality), even if the subject discontinues study drug or discontinues from the study. When the outcome of the pregnancy becomes known, the form should be updated and returned to Alexion or designee. If additional follow-up is required, the investigator will be requested to provide the information.

Pregnancy in itself is not regarded as an AE, unless there is a suspicion that investigational product may have interfered with the effectiveness of a contraceptive medication. However, complications of pregnancy and abnormal outcomes of pregnancy are AEs, and many may meet criteria for an SAE. Complications of pregnancy and abnormal outcomes of pregnancy, such as ectopic pregnancy, spontaneous abortion, intrauterine fetal demise, neonatal death, or congenital anomaly, would meet the criteria of an SAE and therefore should be reported as an SAE. Elective abortions without complications should not be handled as an AE.

Exposure of an infant to an Alexion product during breastfeeding should also be reported on the "Pregnancy Reporting and Outcome/Breast Feeding Form." Any AEs an infant experiences following breastfeeding are to be reported to Alexion or designee.

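### No serum pregnancy test is scheduled between Day -1 and Day 150, so an unrecognised pregnancy may be found late and an unrecognised early loss may go unrecorded

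*Protocol*

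**What the plan says.** **Testing.** Table 4 of Protocol Section 9 has a serum pregnancy test at screening and on Day -1. These two tests gate entry, because exclusion criterion 12 bars a woman with a "Positive serum pregnancy test at screening or on Day -1". After dosing, the Table 5 row "Serum Pregnancy Test" is marked at Visit 13 (Day 150) and Visit 14 (Day 200) only. The 11 visits from Day 8 to Day 120 are blank. Section 15.1.6.7 refers all timing back to Section 9, no footnote adds a test, and the SAP does not mention pregnancy testing.

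**Contraception and antibiotics.** Inclusion criterion 7 requires contraception from screening to at least 6 months after dosing. It warns: "Antibiotic prophylaxis is required during this study, which can compromise the efficacy of hormonal contraception". For women on hormonal methods it recommends, but does not require, an added barrier method while antibiotics are taken. Prophylaxis starts on the evening of Day -1 and ends when CH50 shows normal complement activity. Table 5 places CH50 samples at Day 43 and Day 57, and Section 5.1.4.1 anticipates normalisation at Day 56.

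**Reporting.** Section 16.8 says that "exposure during pregnancy must be recorded and followed". It counts spontaneous abortion among the outcomes to be reported as serious adverse events.

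**The concern.** The interval without a test is also the interval in which a pregnancy would matter most. It holds most of the drug exposure and the anticipated antibiotic period, when the protocol itself says hormonal contraception may be less reliable. A woman who conceives soon after dosing and does not notice meets no scheduled test for about 21 weeks. If such a pregnancy ends early and unnoticed, the Day 150 and Day 200 tests would not reveal it.

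Two things are at stake. One is timely follow-up of an exposed pregnancy. The other is the completeness of serious adverse event capture: incidence of serious adverse events is a safety endpoint (Protocol Section 7.1, SAP Section 2.2), and adverse event assessment is part of the first primary objective.

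**Working it through.** The documents give no figure for the share of exposure elapsed at Day 150, so there is nothing to reproduce. It is derived here.

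**Inputs**
- First post-dose test: Day 150, given as 3576 h in Protocol Section 13.1; 3576 / 24 = 149 days after dosing.
- IV half-life: Section 5.1.1 reports "mean geometric half-life estimates of 32.4 days and 30.8 days following single doses of 200 and 400 mg, respectively". The study dose is 400 mg. Section 8.3.1 adds the variability: "ranged from 30.8 (10.2%) to 32.4 (16.2%) days over the studied doses".
- SC absorption half-life: not documented. Assumed 1 to 10 days.

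**Length of the gap.** Day -1 to Day 150 is 1 + 149 = 150 days; 150 / 7 = 21.4 weeks.

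**IV exposure elapsed**, with mono-exponential decline: share of AUC = 1 - 2^(-t / half-life), t = 149 days.
- 30.8 days: 1 - 2^(-149/30.8) = 1 - 0.035 = 96.5%.
- 32.4 days: 1 - 2^(-149/32.4) = 1 - 0.041 = 95.9%.
- Moving the half-life by one geometric SD, from the stated CVs, gives 95.2% to 97.6% (around 30.8 days) and 93.4% to 97.6% (around 32.4 days).
- A faster early distribution phase after IV dosing would raise these shares.

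**SC exposure elapsed**, one compartment with first-order absorption: share = 1 - [ka·exp(-ke·t) - ke·exp(-ka·t)] / (ka - ke), with each rate equal to ln 2 divided by its half-life.
- Half-life 30.8 days: 96.4% (absorption half-life 1 day) down to 94.8% (10 days).
- Half-life 32.4 days: 95.7% down to 94.0%.

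Across both routes, at the documented half-lives, the share is about 94% to 96%.

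**Share elapsed at existing visits (IV formula)**

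| Visit | Half-life 30.8 days | Half-life 32.4 days |
|---|---|---|
| Day 57 | 71.6% | 69.8% |
| Day 90 | 86.5% | 85.1% |
| Day 120 | 93.1% | 92.2% |
| Day 150 | 96.5% | 95.9% |

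**Blood already drawn.** PK samples are taken at all 11 visits from Day 8 to Day 120. Chemistry is drawn at seven of them: Days 8, 15, 29, 43, 57, 90 and 120.

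**Rough scale, on assumptions only.** The documents do not give the number of women of childbearing potential or a contraceptive failure rate. If there were 10 to 20 such women with 1% to 5% failure per year, over 150/365 = 0.41 years, the expected number of pregnancies would be between 10 × 0.01 × 0.41 = 0.04 and 20 × 0.05 × 0.41 = 0.41. Unrecognised ones would be a fraction of that.

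**The case against.** The strongest reply is that this is a design choice and breaches nothing, and much of it stands.

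- **No contradiction.** A reader might infer that Table 5 conflicts with Section 16.8. It does not. That section sets a duty to report and follow a pregnancy that occurs or comes to light during exposure; it sets no testing frequency. Inclusion criterion 7 meets the antibiotic concern through contraception, not testing.
- **The exposure share is not a risk.** A reader might take the 94% to 96% as the chance that an exposed pregnancy is missed. It is only the share of AUC elapsed by the first post-dose test.
- **Testing cannot reduce exposure.** The drug is given once and Protocol Section 11.7 says it has no antidote. The tests that can prevent exposure, at screening and Day -1, are in place.
- **Other safeguards exist.** Contraception is mandatory, adverse events are monitored continuously and sought by open-ended questions, each visit includes a safety discussion, and physical examinations fall on Days 15, 43, 90 and 120. A pregnancy or loss that the woman recognises should be reported.
- **The existing tests have a plausible purpose.** Days 150 and 200 lie either side of the end of the 6-month contraception period, at about Day 183.

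None of this reaches a pregnancy the woman has not recognised. If it is ongoing at Day 150, it is found then, but late. If it began and ended unnoticed before Day 150, no scheduled test would find it.

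**Conclusion.** The point holds as a modest gap in detection. Serum pregnancy testing is absent for 150 days, covering about 94% to 96% of drug exposure and the anticipated antibiotic period. The consequence is confined to unrecognised pregnancies: ongoing ones may be found up to about 21 weeks late, and early losses may go unrecorded although Section 16.8 would class them as serious adverse events.

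The exposure share rests on mono-exponential decline, on IV half-lives from an earlier single-dose study and, for SC, on assumed absorption half-lives of 1 to 10 days. The conclusion does not depend on where in the range the share lies. The expected number of affected women is small and cannot be sized from the documents.

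The documents do not support stronger conclusions that the protocol contradicts itself, that most exposed pregnancies would be missed, or that the bioavailability objective is affected. This is a cheap improvement with a modest benefit, not a defect that blocks the study.

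**What to change.** Review the Table 5 pregnancy-test row against inclusion criterion 7 and Section 16.8. Add an hCG assay at some of the existing visits between Day 8 and Day 120 where chemistry blood is already drawn, and keep Days 150 and 200. The sponsor should choose the visits. As an illustration, Days 29, 57, 90 and 120 would leave no more than 33 days between tests up to Day 150, compared with 150 days now.

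The change is to one table row and needs no extra visit. It costs a few assays per woman and the follow-up of occasional false positives. hCG is not in the chemistry panel of Section 15.1.6.2, so sample volume must be checked against the laboratory manual before assuming that no extra blood is needed.

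The fix narrows the gap without fully closing it: a conception and very early loss between two monthly tests could still be missed.
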